10.3.4 Reporting of SAEs

SAE reporting to the Sponsor (or representative) via an electronic data collection tool

- The primary mechanism for reporting an SAE to the Sponsor (or representative) will be the electronic data collection tool.
- If the electronic system is unavailable, then the site will use the paper SAE data collection tool (see next section) in order to report the event within 24 hours.
- The site will enter the SAE data into the electronic system as soon as it becomes available.
- After the study is completed at a given site, the electronic data collection tool will be taken off-line to prevent the entry of new data or changes to existing data.
- If a site receives a report of a new SAE from a study participant or receives updated data on a previously reported SAE after the electronic data collection tool has been taken off-line, then the site can report this information on a paper SAE form (see next section) or to the Sponsor (or representative) by facsimile transmission or email.
- Contacts for SAE reporting can be found in the Study Manual.

SAE reporting to Sponsor (or representative) via paper CRF

- Facsimile transmission or email of the SAE paper CRF is the preferred method to transmit this information to the Sponsor (or representative) if the electronic data collection tools are not available.
- In rare circumstances and in the absence of facsimile equipment, notification by telephone is acceptable with a copy of the SAE data collection tool sent by overnight mail or courier service.
- Initial notification via telephone does not replace the need for the Investigator to complete and sign the SAE CRF pages within the designated reporting time frames.
- Contacts for SAE reporting can be found in Study Manual.

10.4 APPENDIX 4: CONTRACEPTIVE GUIDANCE AND COLLECTION OF PREGNANCY INFORMATION

Not applicable.

10.5 APPENDIX 5: OVERDOSE

An overdose (accidental or intentional) with the IMP/NIMP is an event suspected by the Investigator or spontaneously notified by the participant and defined as any dose of study treatment administered to a participant or taken by a participant that exceeds the dose assigned to the participant according to the protocol.

All overdoses (symptomatic and asymptomatic) must be recorded on the overdose form of the CRF within 24 hours of the site becoming aware of the overdose. All study drug-related dosing information must be recorded on the dosing CRF.

The signs and symptoms associated with a symptomatic overdose (serious and/or non-serious) with IMP/NIMP must also be recorded as an AESI on the CRF ([Section 8.3.1](#)).

Asymptomatic overdoses are not considered AEs and should not be recorded as an AE on the CRF.

10.6 APPENDIX 6: COUNTRY-SPECIFIC REQUIREMENTS

Not applicable.

10.7 APPENDIX 7: ADDITIONAL APPENDICES

10.7.1 Definitions of minor and major surgery

Minor surgery is defined as any invasive operative procedure in which only skin, mucous membranes, or superficial connective tissue is manipulated and does not meet the criteria for major surgery (eg, dental extraction of <3 nonmolar teeth). Minor surgical procedures may be performed at a local health care provider institution.

Major surgery is defined as any invasive operative procedure that requires any of the following:

- Opening into a major body cavity (eg, abdomen, thorax, skull)
- Operation on a joint
- Removal of an organ
- Dental extraction of any molar teeth or ≥ 3 nonmolar teeth
- Operative alteration of normal anatomy
- Crossing of a mesenchymal barrier (eg, pleura, peritoneum, dura)

It is recommended that any elective non-dental major surgery be performed at a study site, when possible.

10.7.2 Definitions of minor, moderate, and major bleeding episodes

Minor

- Mild Epistaxis
- Early signs of joint bleeding
- Mild soft tissue bleed

[figure not shown]
Moderate

- Epistaxis with heavy blood flow
- Muscle bleeding
- Gastrointestinal/oral mucosal bleeds
- Gum bleeding after dental extraction
- Hematuria
- Hemarthrosis

Major to life-threatening

- Epistaxis with very heavy blood flow
- Retropharyngeal and pharyngeal bleeding
- Abdominal and retroperitoneal bleeding
- Post-surgical bleeding
- CNS bleeding

10.7.3 Hemophilia joint health score (HJHS)

10.7.4 Washout and blood sampling summary

The following tables summarize the requirements for washout and blood sampling necessary to successfully complete both the washout and PK sampling. If a participant experiences a bleeding episode after receiving the dose of BIVV001 but prior to completing the PK sampling, PK sampling will be stopped at the time of the bleed.

Washout and pk sampling requirements

Screening: all participants
	
Washout
 
 • First attempt: Washout of at least 48 hours before Screening inhibitor test to obtain interpretable test results^a. Repeat this washout if participant treats a bleed prior to 48 hours (follow second attempt). • Second attempt: Conduct same washout as first attempt. • If the second attempt at washout fails, additional attempts may be considered after consultation with the medical monitor^a.

Baseline PK sampling: PK subgroup
	

Day 1 Baseline PK sampling: 12 subjects <6 years of age
	
Washout
 
 • First attempt: Washout of at least 72 hours (3 days); repeat this washout if participant treats a bleed prior to 72 hours (follow second attempt)^a. • Additional attempt(s): Conduct same washout as first attempt^a. • If the second attempt at washout fails, additional attempts may be considered after consultation with the medical monitor. 
PK Sampling
 
 • First attempt: PK sampling period with collection of PK samples (Table 2) to 168 hours (Day 8) is required. If a participant treats a bleeding episode after receiving the dose of BIVV001 for PK evaluation but prior to completing the PK sampling period, PK sampling will be stopped at the time of the bleed and a second attempt (repeat) PK sampling period should be conducted. • Second attempt: Participants are required to undergo a 240 hour (10 Day) washout from the prior BIVV001 dose, which is then followed by the PK sampling period with collection of PK samples (Table 2) to 168 hours (Day 8). • If the second attempt at PK sampling period fails due to the participant treating a bleed prior to collection of the 168-hour (Day 8) sample, the participant will remain in the study but will no longer be included in the PK subgroup. The participant will be replaced in the PK subgroup and will continue with prophylactic BIVV001 dosing regimen.

Day 1 Baseline PK sampling: 12 subjects 6 to <12 years of age
	
Washout
 
 • First attempt: Washout of at least 96 hours (4 days); repeat this washout if participant treats a bleed prior to 96 hours (follow second attempt)^a. • Additional attempt(s): Conduct same washout as first attempt. If the second attempt at washout fails, additional attempts may be considered after consultation with the medical monitor^a. 
PK Sampling
 
 • First attempt: PK sampling period with collection of PK samples (Table 2) to 168 hours (Day 8) is required. If a participant treats a bleeding episode after receiving the dose of BIVV001 for PK evaluation but prior to completing the PK sampling period, PK sampling will be stopped at the time of the bleed and a second attempt PK sampling period should be conducted.

- Second attempt: Participants are required to undergo a 240 hour washout^a after previous dose, which is then followed by the PK sampling period with collection of PK samples (Table 2) to 168 hours (Day 8).
- If the second attempt at PK sampling period fails due to the participant treating a bleed prior to collection of the 168-hour (Day 8) sample, the participant will remain in the study but will no longer be included in the PK subgroup. The participant will be replaced in the PK subgroup and will continue with prophylactic BIVV001 dosing regimen.

Peak and trough sampling: All Participants except PK subgroup at Day 1

Washout

- First attempt: Washout of at least 72 hours (3 days) or 96 hours (4 days) for < 6 yr and 6 to <12 yr participants, respectively; repeat this washout if participant treats a bleed prior to 72 hours and 96 hours for <6 yr and 6 to <12 yr participants respectively (follow second attempt)^a.
- Additional attempts: Conduct same washout as first attempt.
- If the second attempt at washout fails, additional attempt may be considered after consultation with the medical monitor.

PK Sampling

- Collection of sample at trough (immediately pre-injection) and peak at 15 ±3 mins from start of injection. If the participant is being treated for an acute bleeding prior to collection of the peak and trough sample collection, no repeat sampling is needed and the patient will remain in the study and collect peak and trough at the next scheduled visit.

Peak and trough sampling: All Participants after Day 1

Washout

- No washout required. Participants should visit clinic 7 ±1 day after previous dose.
- If the participant has treated a bleeding episode since his last dose, the scheduled visit should be postponed for 7 ±1 day after previous dose.

PK Sampling

[figure not shown]
- Collection of sample at trough (immediately pre-injection) and peak at 15 ±3 mins from start of injection. If the participant treats a bleed prior to collection of the peak and trough sample collection, no repeat sampling is needed and the participant will remain in the study and collect peak and trough at the next scheduled visit.

^a The washout period may be modified at the discretion of the Investigator based on individual PK data and clinical phenotype in consultation with medical monitor

[figure not shown]

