
 To evaluate the efficacy of BIVV001 as a prophylaxis treatment To evaluate the efficacy of BIVV001 in the treatment of bleeding episodes To evaluate BIVV001 consumption for prevention and treatment of bleeding episodes To evaluate the effect of BIVV001 prophylaxis on joint health outcomes To evaluate the effect of BIVV001 prophylaxis on Quality of Life (QoL) outcomes To evaluate the efficacy of BIVV001 for perioperative management 	
 Annualized bleeding rate (ABR) (for treated, for untreated, for all bleeding episodes) and by type and location Percentage of participants who maintain FVIII activity levels over 1%, 3%, 5%, 10%, 15%, and 20% at Day 7 Number of injections and dose of BIVV001 to treat a bleeding episode Percentage of bleeding episodes treated with a single injection of BIVV001 Assessment of response to BIVV001 treatment of individual bleeding episodes based on the International Society on Thrombosis and Haemostasis (ISTH) 4-point response scale Physician's global assessment (PGA) of participant's response to BIVV001 treatment based on a 4-point response scale Total annualized BIVV001 consumption per participant Annualized joint bleeding rate (AJBR) Target joint resolution at Week 52, based on ISTH criteria Change from Baseline to Week 52 in total score and domain scores (eg, swelling and strength) assessed by the Hemophilia Joint Health Score (HJHS) Changes in Haemophilia Quality of Life Questionnaire for Children (Haemo-QoL) total score and physical health domain score from baseline to Week 52 (≥4 years old) and via parent proxy version (≥4 years old) Investigators' or Surgeons' assessment of participant's hemostatic response to BIVV001 treatment on the ISTH 4-point response for surgical procedures scale Number of injections and dose to maintain hemostasis during perioperative period for major surgery Total BIVV001 consumption during perioperative period for major surgery Number and type of blood component transfusions used during perioperative period for major surgery Estimated blood loss during perioperative period for major surgery

Objectives	Endpoints

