8.5 PHARMACOKINETICS

Pharmacokinetic sampling will be conducted as outlined in the sections that follow. Detailed guidelines of washout and PK sampling requirements for baseline and bleeding scenarios are provided in Appendix 7, [Section 10.7.4](#). If a participant has a bleed during the PK time period ([Table 2](#)), the participant's caregiver should enter the bleed into the ePD, contact the Investigator as soon as possible and follow the criteria given in Appendix 7, [Section 10.7.4](#).

The first 24 participants from the 2 age cohorts (12 participants <6 years of age and 12 participants 6 to <12 years of age) will undergo an evaluation of the PK profile of BIVV001 and will be included in the PK subgroup. After completing the baseline PK assessments, these 24 participants will begin QW 50 IU/kg prophylactic treatment with BIVV001. Any participant who does not have adequate PK data will be excluded from the PK analysis. Additional participants may be enrolled to ensure that at least 24 participants have adequate PK data for analysis. The remaining participants will proceed directly to QW prophylactic treatment. Baseline PK sampling can be conducted in other participants at the discretion of investigator through the central laboratory.

During study visits, for reliable PK assessment, PK sampling should not be done via the same intravenous access route as used for the BIVV001 administration.

PK Subgroup: At least 12 participants <6 years of age and at least 12 participants 6 to <12 years of age will undergo PK sampling (up to 168 hours) for BIVV001 activity as follows:

- Dosing at Day 1: single dose of BIVV001 50 IU/kg administered under medical supervision (using a partial vial and actual potency dosing, see [Section 6.1.6.1](#))
- Baseline PK sampling at BIVV001 Day 1: Pre-injection and 15 (± 3) minutes, 3 hours (± 15 minutes), 24 (± 2) hours [Day 2], 72 (± 5) hours [Day 4], and 168 (± 5) hours [Day 8] from the start of the injection

See [Table 2](#) for details of PK sampling of first 12 participants in each age cohort. If a participant has a bleed during the PK time period above, the participant's caregiver should enter the bleed into the ePD and contact the Investigator as soon as possible.

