4.1.1.2 Efficacy period

The efficacy period will be used for the evaluation of bleeding and consumption endpoints. For a participant to have an evaluable efficacy period over the duration of study, he/she must have at least 2 prophylactic dose of study drugs. The efficacy period is defined as the treatment period interrupted for PK periods, surgical/rehabilitation periods (major and minor) and large injection intervals as described below.

Adjustments Due to PK sampling period(s)

For participants undergoing PK sampling after their first dose of BIVV001, the efficacy period starts with the date and time of the first prophylactic dose following the completed PK sampling period (168 hours), and ends with the end of the treatment period as defined in Section 4.1.1.1. That is, if the initial PK sampling period is incomplete due to an aborted collection of blood samples following the PK injection (eg, because of a bleeding episode that required treatment), then the efficacy period will begin following a subsequent fully executed PK sampling period.

Adjustments Due to Surgical/Rehabilitation Periods

For analysis purposes, the efficacy period will be adjusted for all surgical/rehabilitation periods (major and minor). The start and end of the efficacy period are adjusted as follows:

- For all participants, the efficacy period continues up to 1 minute before the start of a surgical/rehabilitation period.
- For participants on a prophylactic regimen following the end of a surgical/rehabilitation period, the efficacy period for the prophylactic regimen re-starts at the first prophylactic dose following the end of the surgical/rehabilitation period.

Statistical Analysis Plan BIVV001-EFC16295 23-Aug-2021 Version number: 1

Bleeding episodes that occur during the surgical/rehabilitation period will be attributed to the surgical/rehabilitation period and hence not counted towards the ABR.

Adjustments Due to Large Injection Intervals

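### Protocol 10.7.4 gives two triggers for stopping baseline PK sampling (any bleed, or only a treated bleed), and SAP 4.1.1.2 gives no efficacy-period start to a PK-sampled child who never completes a PK period

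*Protocol*

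**What the plan says.** **Stopping PK sampling.** The sentence that introduces the tables in Protocol 10.7.4 applies to any bleed: "If a participant experiences a bleeding episode after receiving the dose of BIVV001 but prior to completing the PK sampling", sampling stops at the time of the bleed. The first-attempt rule in both age rows is narrower: "If a participant treats a bleeding episode after receiving the dose of BIVV001 for PK evaluation but prior to completing the PK sampling period". Only then do the rows order a stop and a repeat; for 6 to <12 years, "PK sampling will be stopped at the time of the bleed and a second attempt PK sampling period should be conducted". The second-attempt rule in each row also refers to treating a bleed. Section 8.5 tells the caregiver of a child who bleeds in the PK week to "contact the Investigator as soon as possible and follow the criteria given in Appendix 7", without separating treated from untreated bleeds. Untreated bleeds are a recorded category: the endpoint in Section 3 is "Annualized bleeding rate (ABR) (for treated, for untreated, for all bleeding episodes) and by type and location".

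**After two failed attempts.** 10.7.4 keeps the child in the study: "The participant will be replaced in the PK subgroup and will continue with prophylactic BIVV001 dosing regimen".

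**Start of the efficacy period.** For children with baseline PK sampling, SAP 4.1.1.2 says "the efficacy period starts with the date and time of the first prophylactic dose following the completed PK sampling period (168 hours"). If the initial PK period is aborted, the start moves to after a later, fully executed PK period. The SAP's example of an abort is a bleed that needed treatment. More generally, the same section defines the efficacy period as the treatment period with PK periods, surgical periods and long injection gaps taken out.

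**The concern.** The two parts are separate.

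1. No text ranks the opening sentence of 10.7.4 against the rows, and Section 8.5 sends every bleed in the PK week to 10.7.4. A site that follows the opening sentence for an untreated bleed stops a profile that no added FVIII dose has altered. It loses the 168 h sample and possibly the 72 h sample. The rows then assign no second attempt, because nothing was treated.

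2. A child whose PK period is aborted and never followed by a completed one has no start under the PK-specific rule in SAP 4.1.1.2. ABR and annualized consumption are both computed over the efficacy period, so he would contribute to neither, although he is in the Full Analysis Set and on prophylaxis. If treated bleeds caused the failures, a child who bled is left out, which tends to lower the estimated ABR. If the gap is found late, whether he counts and from when would be decided in an open-label study with his bleeds already known.

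**Working it through.** The plan states no figure to reproduce. The check compares the texts and then sizes each part.

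**Texts side by side**

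| Place | Trigger or start |
|---|---|
| 10.7.4, opening sentence | any bleed: stop |
| 10.7.4, both age rows, first attempt | treated bleed: stop and repeat |
| 10.7.4, both age rows, second attempt | treated bleed: leave the PK subgroup, stay on prophylaxis |
| SAP 4.1.1.2, profile completed | efficacy period starts at the next prophylactic dose |
| SAP 4.1.1.2, profile aborted | efficacy period starts after a later, fully executed PK period |
| Aborted and never completed | no start stated |

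**Inputs**
- Bleeds on prophylaxis with earlier products: annual medians from 1 to below 10 (Protocol 2.2.1). I use 1 to 10.
- Untreated share: not in the documents; assumed 25% to 50%.
- Untreated rate: 25% of 1 to 50% of 10 = 0.25 to 5 per year.
- Treated rate, from the same split: 50% of 1 to 75% of 10 = 0.5 to 7.5 per year.
- Post-dose samples at 15 min, 3 h, 24 h, 72 h and 168 h (Protocol Table 2); 24 children in the PK subgroup.
- Adult half-life at 50 IU/kg: 41.25 h, one-stage assay (Protocol 2.2.3.2). Illustration only, since children may differ.

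**Part 1: untreated bleed in the PK week.** With a constant rate r per year, the chance of a bleed within d days is P = 1 − exp(−r·d/365.25).

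| r | P (3 days) | P (7 days) | of 24, before 72 h | of 24, 72 to 168 h | of 24, total |
|---|---|---|---|---|---|
| 0.25 | 0.0021 | 0.0048 | 0.05 | 0.07 | 0.11 |
| 5 | 0.0402 | 0.0914 | 0.97 | 1.23 | 2.19 |

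These counts hold only if every site follows the opening sentence; if every site follows the rows, the count is zero. The count before 72 h is probably too high, because Protocol 4.3 expects mean FVIII activity above 40% for 3 to 4 days.

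With mono-exponential decay, the share of AUC beyond the last sample is 2^(−t/41.25): about 6% at 168 h, 30% at 72 h and 67% at 24 h.

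**Part 2: a treated bleed in both PK weeks.** Let m = 7r/365.25. With independent weeks, P(both) = (1 − exp(−m))². With gamma variation between children and dispersion 1 (assumed), P(both) = 1 − 2/(1+m) + 1/(1+2m).

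| r | m | P(both), independent | of 24 | P(both), dispersion 1 | of 24 |
|---|---|---|---|---|---|
| 0.5 | 0.0096 | 0.00009 | 0.002 | 0.00018 | 0.004 |
| 7.5 | 0.1437 | 0.0179 | 0.43 | 0.0281 | 0.67 |

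Even at the upper end the most likely number is zero: (1 − 0.0179)^24 = 0.65, and (1 − 0.0281)^24 = 0.51 with dispersion.

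This counts one route only. The SAP names a treated bleed as an example of an abort, and SAP 4.8.1 foresees repeats for other reasons. A profile stopped for an untreated bleed under part 1 and not repeated would also have no start.

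**Weight of one child.** SAP 4.9 plans an interim efficacy analysis of 12 older children at 25 exposure days. The first 12 in that cohort are PK-sampled, so these should be largely the same children. One child is 1/12 = 8.3% there and 1/65 = 1.5% at the end. As an illustration with an assumed contrast (his ABR 10, all others 1), the crude mean with him is (11 + 10)/12 = 1.75 at the interim and (64 + 10)/65 = 1.14 at the end; without him it is 1.00 in both.

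**The case against.** **Part 1.** The opening sentence only introduces tables that hold the working criteria, and every PK-subgroup trigger in those tables refers to treatment. The SAP example agrees, and the investigator is consulted before anything is stopped. All of this stands as evidence of intent. It makes the opening sentence the slip, but no text tells a site to disregard it.

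A reader might infer that the PK results would be biased or the subgroup left short. The documents do not support that. The PK Analysis Set requires adequate sampling as judged by the PK scientist, the end-of-study definition requires profiles with an adequate terminal half-life, and Section 8.5 provides that "Additional participants may be enrolled to ensure that at least 24 participants have adequate PK data for analysis". The cost is a shortened profile and perhaps a replacement child.

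A reader might also want the stop point moved from the time of the bleed to the first FVIII dose given for it. The documents give no ground for calling the present stop point an error. They also do not say whether a bleed by itself changes FVIII activity.

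**Part 2.** The general definition of the efficacy period can serve as a fallback. The child has left the PK subgroup and may well meet the stated minimum of two prophylactic doses. That reading is arguable. But the general definition gives no end for an aborted PK period, and the specific rule points to a later completed one.

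Two stronger readings go too far. One is that every child without a start must have been treated for bleeds in two PK weeks. Aborts can have other causes and a repeat is only recommended, so the direction of bias is a tendency tied to one cause. The other is that the 12 older children are the whole interim efficacy evidence. SAP 4.9 also plans selected efficacy data when the adult/adolescent study is completed. All analyses are descriptive, so no test or error rate is involved.

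**Conclusion.** Both parts hold as minor defects in the stated rules.

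1. The opening sentence of 10.7.4 is broader than every row below it and, if obeyed, shortens profiles without assigning a repeat. The range of 0.1 to 2.2 of 24 profiles rests on bleed rates from earlier products, an assumed untreated share and uniform obedience to that sentence. The adequacy and replacement rules limit the damage.

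2. SAP 4.1.1.2, taken literally, removes from ABR and consumption a treated child who never completes a PK period. Through two treated bleeds the expected number is 0.002 to 0.43 of 24, or up to 0.67 with assumed dispersion 1: most likely none, and at most about one. That child would be 1 of 12 in the older-cohort interim and 1 of about 65 at the end.

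The primary inhibitor endpoint does not use the efficacy period and is not affected. The textual findings are firm. The counts are rough, because the documents give neither an untreated-bleed rate nor a bleed rate for this product in children.

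**What to change.** **Protocol 10.7.4:** in the opening sentence, replace *experiences* with *treats*, so that it matches the rows. Leave the stop-point wording as it is.

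**SAP 4.1.1.2:** add one sentence. If no PK sampling period is completed, the efficacy period starts at the first prophylactic dose after the last aborted PK sampling period, that is, after any 240-hour washout and repeat attempt. Naming the last aborted period keeps the washout and the repeat PK week out of the efficacy period, in line with SAP 4.1.1, which excludes data from PK periods.

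**Cost:** one word by amendment or clarification letter, and one SAP sentence, best added before the first interim efficacy analysis. No extra samples, visits or patients.
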